#### **ICD-3:**

#	Section	Page(s)	Change
1.	General	All	Updated version date in the footer to match the protocol version date. No other changes have been made to this consent as the risks of temsirolimus are not applicable.

Activated: September 14, 2009  
Closed: July 20, 2018

Version Date: 11/07/18  
Amendment: #7

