### 1.2 Primary Aims

#### 1.2.1

To estimate the EFS in children with Stage I (non-PFH, non-SCU) and Stage II (non-SCU) hepatoblastoma treated with surgical resection followed by 2 cycles of C5V.

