Nine (9) stage I PFH patients will be required for AHEP0731. We may enroll up to 12 patients to account for patients who are determined later to be ineligible. These patients will be followed closely for disease and life status. The outcome of these patients will be summarized through survival and EFS curves estimated by the method of Kaplan and Meier. If 2 or more analytic events are observed, the strategy of surgery without any further therapy will identify enrollment to this strategy for possible termination because of insufficient disease control. If this strategy is associated with a long-term event-free survival of 65%, the probability of accepting it is 0.12. If this strategy is associated with a long-term event-free survival of 93%, the probability of accepting it is 0.89.

Toxicity will be reported using CTCAE criteria (version 4). All Grade 3 or 4 or greater non-hematological toxicities as well as any toxicity that requires submission of an CTEP-AERS report as outlined in protocol [section 11.3](#), Table B, will be reported while the patient is on protocol therapy. The frequency of each toxicity type will be quantified as the percent of reporting periods on which the toxicity of the relevant grade is reported. All reporting periods where the patient receives at least one dose of each of the agents in the therapeutic plan for that individual will be included in the denominator for the rate calculation.

Follow-up data will be obtained on all patients considered eligible for the protocol. As part of the study design, slides sufficient to confirm the histological subtype of hepatoblastoma (PFH v. SCU v. neither PFH nor SCU) of all Stage I patients will be submitted to mandatory central review according to the time lines described above. Patients for whom the central review supports the therapeutic approach of the institutional investigator will constitute the analytic subgroup for each of the analyses planned for Stage I patients. The results of this review will be returned for information to the relevant institutional investigator as soon as the assessment becomes available in the COG data system.

Hypothesis 1.1: (Stage I, non-PFH, non- SCU, Stage II, non-SCU [Stratum 2]): Expected Annual Accrual: 9.2 patients per year. Total: 51 patients. We may enroll up to 60 patients to account for patients who are determined later to be ineligible.

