If 7 or more analytic events are observed the strategy of surgery with reduced chemotherapy will identify enrollment to this strategy for possible termination because of insufficient disease control. If this strategy is associated with a long-term event-free survival of 78%, it will be rejected with probability 0.90. If this strategy is associated with a long-term event-free survival of 89%, it will be accepted with probability 0.81. The graph below describes the probability of accepting the strategy as a function of its long-term EFS:

Hypothesis 1.2 (Intermediate-risk patients [Stratum 3]): As of Amendment #3B enrollment to stratum 3 is terminated because sufficient patients have been enrolled to address the hypothesis. The total enrollment to stratum 3 was 105 patients.

*Feasibility of Delivery of C5VD*: The primary measure of feasibility will be rate of death as a first analytic event. All patients who receive at least one dose of the C5VD regimen will be considered evaluable for this endpoint. Any patient who dies on protocol therapy or within 30 days of the termination of protocol therapy of a cause considered possibly, probably or likely related to systemic chemotherapy will be considered to have experienced an on-protocol-therapy death. If five or fewer of the 99 patients experience on-protocol-therapy death, the regimen will be considered feasible for further development. If the regimen is associated with a death-event rate of 3%, that observed for patients who were assigned to chemotherapy on P9645, the regimen will be considered feasible with probability 0.92. If the regimen is associated with a death-event rate of 10%, the regimen will be considered not feasible with probability 0.94. If the sixth on-protocol-therapy death is reported, study enrollment will be suspended. In addition to this, at each report to the DSMC the estimated on-protocol-therapy death rate and its 95% confidence interval will be reported to the phase III DSMC as the cumulative incidence of on-treatment death and the 95% confidence intervals at four and six months.

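### The Stratum 2 rule (flag at 7 or more events in 51 patients) does not have its stated probabilities: acceptance at 89% EFS is 0.67, not 0.81

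*Combined protocol and SAP*

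**What the plan says.** Section 9.2, Hypothesis 1.1, gives the Stratum 2 size as "Expected Annual Accrual: 9.2 patients per year. Total: 51 patients" and adds "We may enroll up to 60 patients to account for patients who are determined later to be ineligible". The 51 is therefore the number the design works with, and 60 is a ceiling that allows for ineligible patients.

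The decision rule is "If 7 or more analytic events are observed the strategy of surgery with reduced chemotherapy will identify enrollment to this strategy for possible termination". Two operating characteristics follow:

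- For a strategy that controls disease poorly, the plan states: "If this strategy is associated with a long-term event-free survival of 78%, it will be rejected with probability 0.90". This is the protection claimed against a bad regimen.
- For a strategy that performs well, it states: "If this strategy is associated with a long-term event-free survival of 89%, it will be accepted with probability 0.81". This is the claimed chance of keeping a good one.

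The plan then refers to a graph of the acceptance probability, which is not in the text available for this review. No other cut-off or sample size for this stratum appears in the document.

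The matching primary aim (1.2.1) is one of estimation: "To estimate the EFS in children with Stage I (non-PFH, non-SCU) and Stage II (non-SCU) hepatoblastoma". The front matter records "Closed: July 20, 2018".

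**The concern.** A count rule in a fixed number of patients determines its own acceptance and rejection probabilities. Here the rule and both probabilities are stated, so they can be checked against each other, and they disagree.

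This is the only accept/reject rule for the stratum in which adjuvant chemotherapy is cut from four cycles to two, and Section 2.3.2 relies on strict stopping rules in justifying that reduction. Readers will judge the accept or reject label by the stated probabilities. If exactly 7 events occur, the written rule rejects the strategy, whereas the rule that the probabilities describe accepts it.

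**Working it through.** **Inputs** (Section 9.2, Hypothesis 1.1): n = 51; flag at X ≥ 7, accept at X ≤ 6; event probability 1 − 0.78 = 0.22 in the unfavourable case and 1 − 0.89 = 0.11 in the favourable case. X is the number of analytic events, X ~ Binomial(51, p), with every long-term event taken as observed.

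**Step 1. Can the plan's figures be reproduced from its own rule?**

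| Rule, n = 51 | Rejection at 78% EFS | Acceptance at 89% EFS |
|---|---|---|
| Stated | 0.90 | 0.81 |
| 7 or more (as written) | P(X ≥ 7; p = 0.22) = 0.952 | P(X ≤ 6; p = 0.11) = 0.673 |
| 8 or more | P(X ≥ 8; p = 0.22) = 0.900 | P(X ≤ 7; p = 0.11) = 0.806 |

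The written rule misses by 5 and 14 percentage points. A cut-off of 8 matches both figures to two decimals. Over cut-offs 3 to 13 and sizes 30 to 69, cut-off 8 with n = 51 is the only pair within 0.01 of both.

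**Step 2. Is the exact binomial the plan's method?** The other rules in Section 9.2 were recomputed the same way.

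| Rule | Computed | Stated |
|---|---|---|
| Stratum 1 (9 patients, accept at ≤ 1) | 0.121, 0.873 | 0.12, 0.89 |
| Stratum 3 (99 patients, accept at ≤ 5) | 0.922, 0.939 | 0.92, 0.94 |
| Stratum 4, two-stage | 0.900, 0.907; early stop 0.435 | 0.90, 0.90; 0.435 |
| Referral (≥ 16 of 25) | 0.115, 0.242, 0.425, 0.630, 0.811, 0.929 | 11%, 24%, 42%, 63%, 81%, 93% |
| OLT (≥ 8 of 14) | 0.395, 0.546, 0.692, 0.816, 0.907, 0.962 | 0.40, 0.55, 0.69, 0.82, 0.90, 0.96 |

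Agreement is to rounding or within 0.01, except for one Stratum 1 figure, which is off by 0.017.

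**Step 3. Other explanations, keeping the cut-off at 7** (rejection at 78% / acceptance at 89%).

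- Another n: no n from 30 to 60 brings both figures within 0.02. The nearest is n = 44, with 0.880/0.795. The ceiling of 60 gives 0.987/0.505.
- Approximations at n = 51: Poisson 0.930/0.669; normal 0.923/0.733; normal with continuity correction 0.945/0.655.
- Only a fraction f of long-term events seen, so p becomes 0.22f and 0.11f: f = 0.95 gives 0.930/0.719; f = 0.90 gives 0.902/0.763; f = 0.87 gives 0.881/0.788; f = 0.85 gives 0.865/0.804. One figure is recovered only by losing the other.
- Continuous monitoring: events only accumulate, so repeated looks up to 51 patients give the same final probability as one look.

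**Step 4. Size of the discrepancy.**

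- At 89% EFS the flag probability is 1 − 0.673 = 0.327, against an implied 1 − 0.81 = 0.19.
- The written rule reaches 0.81 acceptance only at a true EFS of 90.7%, and already reaches 0.90 rejection at 80.3%.
- At 84% EFS, the 5-year figure Section 2.3.2 gives after four cycles, the flag probability is 0.728 with cut-off 7 and 0.583 with cut-off 8.
- At 91% EFS, the figure the same section gives for Stage I non-PFH patients, the written rule accepts with probability 0.828.

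**The case against.** The strongest reply is that 0.67 is conditional. The plan speaks of long-term EFS but analyses after five years of enrollment plus one more year, by which time it expects most, not all, events. Suppose follow-up is spread evenly over 1 to 6 years and failures occur at an assumed hazard of 0.8 per year. The fraction seen is then 1 − (e^−0.8 − e^−4.8)/(0.8 × 5) ≈ 0.89, and the written rule gives about 0.90/0.77. A hazard of 1.0 gives a fraction of about 0.93 and 0.92/0.74. The false-flag rate could then be nearer 1 in 4 than 1 in 3. The one other rule based on EFS events, Stratum 1, is also where the binomial fits least well: 0.873 against "If this strategy is associated with a long-term event-free survival of 93%, the probability of accepting it is 0.89". That caution stands as a limit on the precision of 0.67. It does not rescue the text: no constant fraction tried yields both figures, and a 0.017 gap in Stratum 1 is far smaller than the 0.14 gap here.

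A second reply is that if 8 was intended, restating the probabilities for 7 would enshrine a typing error. That is fair, and it is why the design calculation should be retrieved first. Without it, relaxing a cut-off after accrual has closed is the harder change to defend.

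A third reply is that little now depends on the rule. It only flags for possible termination, errs on the protective side at 78% EFS, and leaves the EFS estimate untouched. All of this is true, and it confines the effect to how the result is labelled and reported.

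**Conclusion.** The concern holds. With 51 evaluable patients and all long-term events observed, the written rule rejects with probability 0.95 at 78% EFS (stated 0.90) and accepts with probability 0.67 at 89% EFS (stated 0.81). The stated pair is that of a cut-off of 8. An off-by-one between the largest acceptable count and the flagging count is the likely source, but without the design calculation or the graph it cannot be confirmed.

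The written rule is stricter than described, giving better protection against a poor strategy and more false flags of a good one. It must be corrected because a decision rule for a primary-aim stratum and its published error rates contradict each other, and a count of exactly 7 would reverse the label.

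**What to change.** Retrieve the original design calculation and the acceptance graph, and reconcile the cut-off with its probabilities.

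- **Default:** keep 7 or more and restate the properties as 0.95 rejection at 78% EFS and 0.67 acceptance at 89% EFS, noting that these assume complete observation of events in 51 evaluable patients.
- **Only if the design calculation shows that 8 was intended:** correct the cut-off to 8, keep 0.90 and 0.81, and document the evidence and whether the event count was known at the time.
- Check the acceptance curve against whichever rule is kept, and report the observed event count with the rule.

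The default costs two numbers in the text and a check of one figure, with no patients or data. Its price is a less favourable acceptance probability on record. Moving to 8 is not a neutral edit, because it loosens the rule after accrual closed.

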#### 4.2.2.2

**Patients < 10 kg will have dosing in mg/kg for all agents.**

#### 4.2.2.3

Filgrastim (G-CSF) should not be given initially and should only be administered prophylactically if there is either a 1 week delay in the administration of chemotherapy because of neutropenia or if the patient requires hospitalization for fever and neutropenia or for sepsis.

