#### 4.5 Treatment for Intermediate-Risk Patients (Stratum 3 - Regimen F)

**Note: Stratum 3 has been closed to accrual as of 03/12/12.**

All patients with Stage I SCU, Stage II SCU, and Stage III disease will be treated with Regimen F (C5VD). Patients will receive 4 cycles of therapy repeated every 21 days, followed by surgical resection of the tumor or liver transplant (OLT). Patients whose tumors are removed surgically or by OLT after Cycle 4 will receive 2 post-operative cycles of chemotherapy. Patients may have their tumor removed if deemed feasible after 2 cycles of chemotherapy but will then receive 4 cycles of post-operative chemotherapy. **All intermediate-risk patients will receive a total of 6 cycles of chemotherapy.** Patients whose tumors remain unresectable after 4 cycles will be considered off protocol therapy, but will continue to be followed on the AHEP0731 off protocol therapy follow-up CRF. These patients can at the discretion of the primary physician. Additional pre-operative cycles of chemotherapy after Cycle 4 are **NOT** permitted in an attempt to make the tumor resectable or if a liver is not available for transplantation. Patients with progressive disease at any time are off-protocol therapy.

Tumors that are unresectable at diagnosis should be referred to a surgical center with expertise in pediatric liver transplant and “extreme” liver resection as soon as possible. Optimally for planning purposes, this liver transplant consultation should be obtained but at the latest it should be done following the first 2 cycles of neoadjuvant chemotherapy. The consent for the PLUTO registry should be obtained within one month of undergoing liver transplant and is usually obtained by the liver transplant team.

For the purposes of this study, consultation will be defined and may be accomplished in one of two ways:

- The FIRST TIME the patient is seen face to face by the transplant physician/team in the same institution or another institution.
- The FIRST TIME radiographic films and referral material are sent to the transplant physician/team at the same or another institution and are formally reviewed by the transplant physician/team.

The transplant physician/team will communicate the result of this consultation back to the referring physician.

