##### 4.5.1 CISplatin: IV over 6 hours

100 mg/m^2/dose (3.3 mg/kg/dose for patients < 10 kg) on Day 1.

Recommended hydration and administration guidelines:

Urine specific gravity should be < 1.010 prior to starting cisplatin.

Hours -2 to 0: Prehydrate with 300 mL/m^2 D5 ½ NS + MgSO4 8 mEq/L + KCL 20 mEq/L.

Hours 0-6: Infuse CISplatin + mannitol 8000 mg/m^2 in 750 mL/m^2 NS @ 125 mL/m^2/hr.

Hours 6- 24: D5½NS+ MgSO4 8 mEq/L + KCL 20 mEq/L to run at 125 mL/m^2/hr.

4.5.2 5-Fluorouracil: Slow IV Push over 2-4 minutes

600 mg/m^2/dose (20 mg/kg/dose for patients < 10 kg) on Day 2.

4.5.3 VinCRISTine: IV Push over 1 minute or infusion via minibag as per institutional policy

1.5 mg/m^2/dose (0.05 mg/kg/dose for patients < 10 kg) [Maximum dose: 2 mg] on Days 2, 9 and 16.

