4.5.4 DOXOrubicin: IV over 15 minutes

30 mg/m^2/dose (1 mg/kg/dose for patients < 10 kg) on Days 1 and 2.

It is suggested that DOXOrubicin be administered through the tubing of rapidly infusing solution of D5W or 0.9% NaCl and that it is infused into a large vein.

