### 5.2 Doxorubicin

#### 5.2.1 Mucositis

If the patient develops Grade 3 or 4 mucositis that resolves to  $<$  Grade 2 by Day 1 of the next cycle, no dose adjustments will be made in chemotherapy. If the patient develops Grade 3 or 4 mucositis that is NOT attributable to infectious etiology AND recovery to  $<$  Grade 2 does not occur by Day 1 of any cycle, reduce the dose of doxorubicin in the next cycle by 25% to  $22.5 \text{ mg}/\text{m}^2/\text{dose}$  ( $0.75 \text{ mg}/\text{kg}/\text{dose}$ ). If subsequent chemotherapy is tolerated without the recurrence of Grade 3 or 4 toxicity, then resume full dose in the next cycle.

If the patient receives the 25% reduced dose and again has Grade 3 or 4 mucositis that is NOT attributable to infectious etiology AND recovery to  $<$  Grade 2 does not occur by Day 1 of the next cycle, further reduce the dose of doxorubicin in the next cycle to  $15 \text{ mg}/\text{m}^2/\text{dose}$  ( $0.5 \text{ mg}/\text{kg}/\text{dose}$ ). If subsequent chemotherapy is tolerated without the recurrence of Grade 3 or 4 toxicity, then escalate to  $22.5 \text{ mg}/\text{m}^2/\text{dose}$  ( $0.75 \text{ mg}/\text{kg}/\text{dose}$ ). If subsequent chemotherapy is tolerated without the recurrence of Grade 3 or 4 toxicity, then resume full dose in the next cycle.

If the patient experiences Grade 3 or 4 toxicity with the 50% dose reduction, the doxorubicin should be omitted from subsequent cycles.

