#### 5.3.2 Change in Renal Function

If the serum creatinine increases to greater than the maximum serum creatinine for age (see [Section 3.2.5.1](#) for threshold creatinine values table), check a creatinine clearance or GFR.

No dose reductions in cisplatin will be made for a decrease in the baseline GFR or creatinine clearance as long as the value remains  $> 60$  mL/min/1.73 m^2. Omit cisplatin therapy from a cycle of therapy if GFR or creatinine clearance is  $< 60$  mL/min/1.73 m^2. If cisplatin is held for a cycle of therapy, repeat the study prior to next cycle. Resume therapy at full dose if GFR or creatinine clearance  $> 60$  mL/min/1.73 m^2.

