Since the addition of doxorubicin to C5V may affect the delivery of all the agents in the combination, we will characterize the amount of each agent that can be delivered during the first four cycles of therapy and the actual amount of doxorubicin delivered on protocol therapy. During the first four cycles, the total dose of each agent administered will be collected, along with the patient's height and weight. The average amount of each drug, calculated as dose per meter squared will be calculated and a lower 95% confidence bound on the true average dose delivered will be calculated assuming a normal distribution of delivered dose. In addition the total doxorubicin dose, in milligrams per meter squared will be calculated for each patient as well as the average and the 95% confidence interval for this amount. This will be used in planning subsequent trials.

Hypothesis 1.3: (Stage IV [Stratum 4]): Expected Annual Accrual: 16 patients per year. Total: 43 patients (to account for patients who may be later determined to be ineligible.)

Prior to Amendment 3B, VI therapy was evaluated in stage IV patients. No patient assigned to VI experienced early progression. All patients evaluated for the VIT combination, therefore, will be evaluated only for response as defined in Section 10 of the protocol.

[figure not shown]
Disease status at the end of two cycles of therapy (or earlier in the case of early progressive disease) will be the endpoint for evaluable patients.

A patient will be considered evaluable if the individual is eligible, receives at least one dose of each agent in the combination being tested and is not removed from protocol therapy for reasons other than toxicity or disease progression. Any evaluable patient who has a CR or PR according the criteria prescribed [Section 10](#) of the protocol will be considered a 'responder'. All other evaluable patients will be considered non-responders. Patients will be enrolled in two stages according to the design specified below:

Number of Evaluable Patients Enrolled	Results	Decision
Stage I: 22 Evaluable Patients	9 or fewer responders	Terminate the trial with the conclusion the regimen does not demonstrate sufficient disease control
	10 or more responders	Continue to the next stage and enroll 19 more patients
Stage II: 19 Evaluable Patients (Total of 41)	Cumulatively 22 or fewer responders	Terminate the trial with the conclusion the regimen does not demonstrate sufficient disease control

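### The C5VD delivered-dose summary pools mg/m² over children dosed per m² and children under 10 kg dosed per kg; percent of the full protocol dose should be added

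*Combined protocol and SAP*

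**What the plan says.** Section 9.2, Hypothesis 1.2, judges the feasibility of C5VD mainly by deaths on protocol therapy. A supporting summary then describes drug delivery. Total administered dose per agent over cycles 1-4 is collected with height and weight, and: "The average amount of each drug, calculated as dose per meter squared will be calculated and a lower 95% confidence bound" is reported, assuming normality. Total doxorubicin in mg/m² is summarised with a mean and 95% confidence interval. The results are meant for planning later trials. No target dose is set, the summary is not split by dosing basis, delivery is not compared with the protocol dose, and nothing is said about children who start fewer cycles.

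The treatment sections use two dosing bases. Section 4.2.2.2 states: "Patients < 10 kg will have dosing in mg/kg for all agents". In Regimen F, cisplatin is 100 mg/m² or "3.3 mg/kg/dose for patients < 10 kg) on Day 1" and doxorubicin is 30 mg/m² or "1 mg/kg/dose for patients < 10 kg) on Days 1 and 2". Fluorouracil (600 mg/m² or 20 mg/kg) and vincristine (1.5 mg/m² or 0.05 mg/kg) follow the same pattern. Vincristine is also capped: "Maximum dose: 2 mg] on Days 2, 9 and 16".

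Doses can also fall for toxicity. For mucositis, Section 5.2.1 says to "reduce the dose of doxorubicin in the next cycle by 25% to" 22.5 mg/m². For renal function, Section 5.3.2 says: "Omit cisplatin therapy from a cycle of therapy if GFR or creatinine clearance is" below 60 mL/min/1.73 m². Treatment can end early for surgical reasons (Sections 4.5 and 8.1): "Patients whose tumors remain unresectable after 4 cycles will be considered off protocol therapy".

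**The concern.** The question behind the summary is whether adding doxorubicin makes the combination harder to deliver. Mean mg/m² answers it only if every fully treated child records the same mg/m². Here a child under 10 kg who receives everything prescribed records well below the m² dose, by design. One pooled mean therefore mixes three things: the weight mix of the stratum, doses reduced or omitted for toxicity, and, for total doxorubicin especially, cycles never started.

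The summary supports primary aim 1.2.2 (feasibility of adding doxorubicin). A later team could read a low mean or a low confidence bound as poor tolerance when it only shows that many patients were small. It could also dismiss a real shortfall as a weight effect. mg/m² is a valid measure of exposure; the gap is that nothing beside it measures delivery.

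**Working it through.** **The plan's own figures.** The death rule (5 or fewer of 99) reproduces with the exact binomial: P(X ≤ 5 | 99, 0.03) = 0.922 against the stated 0.92, and P(X ≥ 6 | 99, 0.10) = 0.939 against 0.94. Full doxorubicin on the m² basis is 6 cycles × 2 doses × 30 = 360 mg/m², the cumulative maximum given in Section 2.3.3. The delivered-dose summary has no stated figure to reproduce.

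**Inputs.** The doses come from Sections 4.5.1 to 4.5.4. The documents give no body-surface formula and no heights, so I assume BSA = √(kg × cm / 3600) and typical heights for weight.

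**When the two bases agree.** For doxorubicin, fluorouracil and vincristine the mg/kg dose equals the m² dose when kg/BSA = 30 (30/1, 600/20, 1.5/0.05). For cisplatin the value is 100/3.3 = 30.3. Under the assumed formula, kg/BSA = 30 requires height in cm = 4 × weight in kg, which is 39.6 cm at 9.9 kg. Essentially every child under 10 kg is taller than that, so the protocol's own doses fix the direction of the effect.

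**One child, every dose given in full.**

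| Weight, assumed height | kg/BSA = doxorubicin mg/m² per dose | % of 30 | Cisplatin mg/m² (= % of 100) |
|---|---|---|---|
| 5 kg, 58 cm | 17.6 | 59 | 58.1 |
| 8 kg, 69 cm | 20.4 | 68 | 67.4 |
| 9.9 kg, 75 cm | 21.8 | 73 | 71.9 |

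**Three sources that look alike.**
- The fully dosed 8 kg child records 20.4 mg/m² per doxorubicin dose, below a larger child reduced by 25% for mucositis (22.5). At 8 kg, heights of 65.5 to 72.5 cm give 21.0 to 19.9, so the ordering holds.
- Over six cycles the 8 kg child totals 12 × 20.43 = 245 mg/m². A larger child fully dosed but taken off therapy as unresectable after cycle 4 totals 4 × 60 = 240. The first received 100% of the planned treatment; the second received 100% of the cycles started but 67% of those planned.
- Over four cycles, full delivery with 40% of children under 10 kg averaging 70% of the m² dose gives 240 × (0.6 + 0.4 × 0.70) = 211 mg/m². A true 12% shortfall with no child under 10 kg gives 240 × 0.88 = 211 mg/m².

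**Cohort mean under full delivery.** Mean % of the m² dose = 1 − s × (1 − r), where s is the share under 10 kg and r is those children's average ratio. Neither is in the documents.

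| s | r = 0.65 | r from 0.60 to 0.70 | Six-cycle doxorubicin at r = 0.65 (full 360) |
|---|---|---|---|
| 10% | 96.5% | 96-97% | 347 |
| 20% | 93% | 92-94% | 335 |
| 30% | 89.5% | 88-91% | 322 |
| 50% | 82.5% | 80-85% | 297 |

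**The bound inherits the problem.** With n = 99, s = 0.30, r = 0.70 and nothing missed, four-cycle doxorubicin has mean 240 × 0.91 = 218.4 and SD 240 × 0.30 × √(0.3 × 0.7) = 33.0, ignoring spread within each weight group. The one-sided lower 95% bound is 218.4 − 1.645 × 33.0/√99 = 213 mg/m², although delivery is complete.

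**Vincristine cap.** Above 2/1.5 = 1.33 m² the cap acts the same way. At 1.7 m² the full dose is 2/1.7 = 1.18 mg/m², or 78% of 1.5.

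**The case against.** The plan promises the amount delivered, mean mg/m² reports exactly that, and exposure including small children dosed by the protocol's own rule is useful for later trials. On this view percent of protocol dose is a different quantity and a matter of preference. That mg/m² is valid, that no threshold depends on it and that the death rule is untouched all stand, and they keep the point minor. But the stated motive is the effect of doxorubicin on delivery, which mg/m² alone cannot show here.

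The cohort effect rests on an unknown share and an assumed average. This also stands: with few children under 10 kg the effect is small, and children clustered near 10 kg could average up to about 73%, milder than the 65% used above.

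The cost may be understated, because Section 9.2 mentions total dose rather than mg per cycle, and the case report forms are not in the documents. Mg per cycle is not needed, however: total administered mg can be divided by the full protocol dose summed over the relevant cycles. That sum needs the cycles started and the height and weight at each cycle, which Section 7.4 requires as an evaluation.

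Finally, a split at 10 kg would deal with most of the weight effect. It would, but it would not separate toxicity from early stopping within either group. Removal reasons and toxicity are recorded elsewhere, but nothing planned links them to dose.

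**Conclusion.** The concern holds, as a minor one. As planned, the summary cannot tell dosing by design from doses reduced or omitted for toxicity, or, for total doxorubicin, from early stopping. The direction follows from the protocol's doses for essentially any child under 10 kg. The single-child size, about 58-73% of the m² dose with nothing missed, rests on the assumed body-surface formula and heights. The size in the pooled mean, from about 97% down to 80% over shares of 10-50%, is conditional on a share and an average ratio that the documents do not give. The feasibility decision and every other decision rule stay as they are, and no dosing rule is questioned.

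**What to change.** Add to the SAP, for each patient and agent, administered mg as a percentage of the full, unreduced protocol dose.

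- **Reference dose:** the mg/kg or mg/m² rule and any cap that applied at each cycle, before any toxicity modification. The weight at the start of the cycle decides the rule, so a child who crosses 10 kg is handled. Using the toxicity-reduced dose as reference would hide the effect being studied.
- **Main denominator:** cycles started, over cycles 1-4 for each agent and over all started cycles for doxorubicin. An agent omitted in a started cycle counts as zero for that cycle. Report the mean and lower 95% bound.
- **Second denominator:** cycles planned (four, or six for total doxorubicin), with the number stopping early by reason: toxicity, progression, unresectable tumor, failure to resume within 42 days of resection, other.
- **Existing summaries:** keep mg/m² as the exposure measure, shown separately for under 10 kg and for 10 kg or more.

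A fully dosed child then scores 100% at any weight, and early stopping is neither hidden nor counted as dose reduction. The cost is SAP wording and a small amount of extra analysis. Administered dose, height and weight are already planned; the team should confirm that the height and weight from each cycle are in the database. Stratum 3 is closed to accrual, so treatment and enrollment do not change.
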